6.2.4 Health-Related Quality of Life

Subjects' health-related quality of life and health utility values will be measured using the EORTC QLQ-C30. A PRO information sheet will be provided and completed by the study nurse/investigator at each visit in which the protocol requires the questionnaires to be administered, whether or not the questionnaire was completed by the subject, in order to document information on questionnaire assessment such as questionnaire completion, date of completion, if assistance was needed, and reasons for non-completed questionnaires.

The EORTC QLQ-C30 includes 5 functional scales (physical, role, emotional, social, and cognitive functioning), 3 symptom scales (fatigue, pain, and nausea and vomiting), a global health status scale, and a number of single items assessing additional symptoms (dyspnea, sleep disturbances, constipation, and diarrhea), and perceived financial impact.

For the majority of the EORTC QLQ-C30 items a 4-point Likert-type response scale is used. The only exception is the global health status/quality of life scale in which a 7-point Likert-type scale is used. For ease of interpretation, all scales and individual item responses are linearly converted to a 0 to 100 scale. For the functional and global quality of life scales a higher score represents better level of functioning. However in regard to symptom scales and single items a higher score reflects a greater degree of symptomatology. Summary statistics and changes from baseline by visit will be provided for EORTC QLQ-C30 for day 1 of each cycle, end of treatment visit and active follow-up based on the efficacy analysis set.

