- I: For monitoring purposes of atezolizumab, blood (plasma) samples will be collected at the following time points: at Cycle 1 Day 1: pre-dose, 1 (EOI), 4 and 8

Integrated Clinical Study Protocol No. BAY 1163877 / 19131 Part A

23 MAY 2023 Version 6.0 Page: 92 of 181

Table 9–2: Schedule of evaluations: Treatment and follow-up periods

hours post-dose; and at Cycle 1 Day 15: approximately 336 hours post-dose.

- m: From signing of PI/ICF for study treatment eligibility up to 30 days after the last administration of study treatment, all concomitant medications (including start/stop dates, dose, frequency, route of administration and indication) must be recorded in the patient's source documentation, as well as on the appropriate pages of the eCRF.
- n: To have complete control over the distribution and use of the study drug, the drug accountability must be performed before new medication is handed out to the patient. Return of rogaratinib and diary at EOT visit.
- o: Patients will receive their initial single-dose of 800 mg rogaratinib in the morning of Cycle 1 Day 1, followed by serial PK blood sampling for 8 hours and a second dose of 800 mg rogaratinib in the evening. Rogaratinib will be administered continuously twice daily on all 21 days in each cycle. Oral administration of the morning dose of rogaratinib on Cycle 1, Days 1, 2, 8 and 15, and on Day 1 of subsequent cycles will be done with a member of the site.
- p: The radiological evaluation must include computed tomography (CT) or magnetic resonance imaging (MRI) of the chest, abdomen and pelvis with contrast media. Tumor assessments (CT or MRI) are to be done every 9 weeks (± 7 days) starting from Cycle 1 Day 1 until confirmed radiological disease progression or end of the study. After primary completion, scans will be performed every 14 weeks (±14 days). A minimum of at least 9 weeks from start of treatment is mandatory for the 1st "on treatment" tumor assessment. Formal efficacy assessment will be done according to RECIST v1.1. iRECIST will be assessed as exploratory endpoint.
- q: Radiological tumor evaluation (within 14 days after permanent discontinuation of study treatment). This is not necessary if the previous tumor evaluation was performed within 4 weeks (up to week 18) or within 7 weeks (beyond week 18).

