10.3.7 Patient-reported outcomes (PRO)

PRO data as measured by the EORTC QLQ-C30 will be analyzed to assess differences in health-related Quality of Life (HRQoL) and health utility values using all available data. The scoring of the PRO endpoints and handling of missing data will be detailed in the statistical analysis plan.

PRO data will be summarized using descriptive statistics and will be graphically displayed if appropriate. Further statistical analyses may be conducted.

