4.3 Handling of Missing Data

Missing data will not be replaced. Analyses will be performed considering all data observed for the respective analysis sets.

All missing or partial data will be presented in the subject data listing as they are recorded on the Case Report Form.

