5.1 Assignment of analysis sets

Final decisions regarding the assignment of subjects to analysis sets will be made during the review of study data and documented in the final list of important deviations, validity findings and assignment to analysis set(s) (see section **4.6**).

All subjects who signed the informed consent form (ICF) for FGFR testing will be included in the 'All enrolled subjects' evaluations. All subjects assigned to treatment will be included in the 'All subjects assigned to treatment' evaluations.

Safety analysis set (SAF)

All subjects who received at least one dose of study drug (i.e. rogaratinib or atezolizumab) and have post-treatment safety data available will be included in the safety evaluation.

MTD analysis set (MTD)

All subjects who completed Cycle 1 and who took at least 80% of the required total dose (protocol-defined dose reductions will not be considered incompliant) of either study drug (rogaratinib or atezolizumab) during Cycle 1 or discontinued during Cycle 1 due to a DLT will be included in the MTD evaluation.

Only subjects from the dose selection part are to be considered for the MTD analysis set.

Efficacy analysis set (EFS)

All subjects who have received at least one dose of study drug and who have post-baseline efficacy data available will be included in the efficacy evaluation.

Pharmacokinetics analysis set (PKS)

All subjects who have received at least one dose of study drug and with at least one valid concentration after first dosing and no important protocol deviations affecting the validity will be included in the PK evaluation.

6. Statistical Methodology

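### SAP 6.2.4 ties the QLQ-C30 summaries to the efficacy analysis set although protocol 10.3.7 uses all available data, so some completed early questionnaires can be dropped

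*SAP*

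**What the plan says.** Protocol 10.3.7 states that the QLQ-C30 data "will be analyzed to assess differences in health-related Quality of Life (HRQoL) and health utility values using all available data". It names no analysis set. What it delegates is limited: "The scoring of the PRO endpoints and handling of missing data will be detailed in the statistical analysis plan".

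SAP 6.2.4 presents summary statistics and changes from baseline by visit for "EORTC QLQ-C30 for day 1 of each cycle, end of treatment visit and active follow-up based on the efficacy analysis set".

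SAP 5.1 defines that set as "All subjects who have received at least one dose of study drug and who have post-baseline efficacy data available". It does not say which data qualify. The safety analysis set in the same section is "All subjects who received at least one dose of study drug (i.e. rogaratinib or atezolizumab) and have post-treatment safety data available".

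SAP 4.3 does not replace missing data and adds: "Analyses will be performed considering all data observed for the respective analysis sets". Observed data are therefore used, but only within the chosen set.

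On timing, the questionnaire is completed at screening, on Day 1 of every 21-day cycle, at the end-of-treatment visit and at the safety visit (protocol 9.7.2). For the first on-treatment tumor assessment, protocol Table 9–2 says: "A minimum of at least 9 weeks from start of treatment is mandatory for the 1st".

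**The concern.** Patient-reported outcome is an exploratory objective in its own right. Under SAP 6.2.4, however, entry to its tables depends on efficacy data and not on a completed questionnaire. Those efficacy data may arise weeks after the questionnaire, and whether they arise can depend on how the patient fares. A patient can have valid answers at Cycles 2 and 3 and still be removed from those visits because of something that happened, or failed to happen, later.

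Two things are at stake. The SAP departs from the protocol on which data are analyzed. Also, the early means and changes from baseline, which cover the period when tolerability is first felt, may describe a selected group. Safety tables run on the safety analysis set, so the same patient's early toxicity would be reported while the quality-of-life answers would not.

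**Working it through.** **1. Is there a stated figure to reproduce?** The documents give no sample size, effect size or expected exclusion rate for the QLQ-C30. The nearest figures are in protocol 10.4: 26 evaluable patients, 15% dropout and about 30 patients in total. 26 / 0.85 = 30.6, which agrees with about 30. These figures concern evaluability for response.

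**2. Visit days.** Cycle c, Day 1 falls on day 1 + 21 × (c − 1): days 1, 22, 43 and 64 for Cycles 1 to 4. Nine weeks is 63 days, so the first scheduled scan falls on day 64. Three Day 1 questionnaires precede it. Under SAP 4.5.1 the baseline is the last value before administration, so the Cycle 1 questionnaire can serve as baseline. The change-from-baseline tables are then exposed at Cycles 2 and 3, and at the end-of-treatment and safety visits for the same patients.

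**3. Who can fall outside the set?** The documents foresee such patients. Protocol 6.4.2 allows replacement of patients without an efficacy assessment, and SAP 6.1.2 plans extra tables if the efficacy set differs from the safety set. The routes are:
- withdrawal of consent to the study, after which no study procedure is allowed (protocol 6.4.1.3);
- loss to follow-up;
- an early stop where the end-of-treatment scan is waived. Through week 18 that scan is unnecessary if the previous tumor evaluation was within 4 weeks (Table 9–2, footnote q). If the baseline scan counts as that evaluation, a patient scanned 2 days before treatment, answering on day 22 and stopping on day 24 needs no scan. Follow-up scans are then still planned, but end when new systemic therapy starts.

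**4. How many?** This depends on the undefined entry term. If only a post-baseline tumor assessment counts, the routes above apply, and so does death before a scan. If clinical progression, death or survival status also counts, few or none are excluded.

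**5. Size of the shift.** Let f be the share of patients answering at a visit who are outside the set, R the mean of those retained and E the mean of those excluded. The full mean is (1 − f)R + fE, so the reported mean differs from it by R − [(1 − f)R + fE] = f(R − E).

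The documents give neither f nor R − E. Assuming 30 patients answer and scores run from 0 to 100 with higher better:

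| Excluded of 30 | Gap −10 | Gap 10 | Gap 20 | Gap 30 |
|---|---|---|---|---|
| 1 | −0.33 | 0.33 | 0.67 | 1.0 |
| 3 | −1.0 | 1.0 | 2.0 | 3.0 |
| 5 | −1.67 | 1.67 | 3.33 | 5.0 |

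For example, 1/30 × 10 = 0.33 and 5/30 × 30 = 5.0. A gap of 0 gives 0. On symptom scales, where higher is worse, the signs reverse.

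**6. After the change.** With all treated patients' questionnaires used at each visit, f = 0 for this restriction and so is the shift.

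**The case against.** A reader might infer that anyone leaving before week 9 is dropped. The documents do not support that. Protocol 9.4 has scans repeated whenever progression is suspected, an end-of-treatment scan is planned within 14 days of stopping, and until primary completion patients who stop without radiological progression continue to be scanned. A patient who answers on day 43 and then stops has a baseline scan at least 42 days old, so the 4-week waiver cannot apply and a scan is due.

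The entry term may also be wider than a scan. Protocol 9.4 derives efficacy variables from survival follow-up as well as imaging, and protocol 9.6.1.3 follows deaths for efficacy. In the SAP, progression-free survival counts clinical progression and death. Its response-rate and time-to-progression rules also provide for subjects with no assessment, within analyses that by default run on the efficacy set. On that reading a patient who dies before a scan stays in. This narrows the affected group considerably. It does not remove the contradiction with protocol 10.3.7, and the lack of a definition is a further reason to amend.

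It is also fair to say that the questionnaires do not vanish: protocol 10.1 lists all data, exclusions from each set are tabulated with reasons, and a PRO sheet records completion. But the planned summaries would still omit them.

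Finally, a rule requiring a baseline and at least one later questionnaire would itself select patients in a way that protocol 10.3.7 does not state. That is right, and the fix avoids it.

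**Conclusion.** The mismatch stands: the protocol calls for all available data, and the SAP makes inclusion depend on a later, outcome-related event. The SAP was written against protocol version 4.0, but the change tables for versions 5.0 and 6.0 list no change to 10.3.7, so they do not explain the difference.

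The consequence is possible bias of unknown size. Some treated patients with completed questionnaires can be dropped, perhaps few. The 0.3 to 5 point range is only an illustration, resting on an assumed 1 to 5 of 30 excluded and an assumed gap of 10 to 30 points.

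Two stronger statements are tempting. One is that early quality of life will look too good. This is plausible, because patients lost before any efficacy data are often sicker, but the documents give no scores for such patients and the sign follows the assumed gap. The other is that the 15% dropout in protocol 10.4 (4.5 of 30) measures the excluded share. It does not: it inflates the number evaluable for response, and patients replaceable for efficacy include those under 80% of dose in two cycles, who may well have scans.

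The summaries are descriptive and exploratory in a single-arm study. No primary conclusion, dose decision or sample size changes. The point is worth correcting because the correction is simple and restores agreement with the protocol.

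**What to change.** In SAP 6.2.4, replace the efficacy analysis set by the safety analysis set, using all questionnaires available at each visit. Report changes from baseline for subjects with a baseline value and a value at that visit. Show the numbers completed and expected at each visit; the PRO sheet in the same section already records completion and reasons for non-completion. The efficacy-set version may stay as a sensitivity analysis, and SAP 5.1 should state what counts as post-baseline efficacy data.

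The cost is one sentence in SAP 6.2.4, one clarification in SAP 5.1 and, if tables already exist, a rerun on collected data. There is no burden on patients or sites.

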6.3 Pharmacokinetics/ Pharmacodynamics

6.3.1 Biomarker/ Pharmacodynamics

Retrospective exploratory biomarker/ pharmacodynamic data may be summarized using descriptive statistics and may be graphically displayed if appropriate. All pharmacodynamics analysis may be performed on the SAF population. The correlation between biomarker or pharmacodynamic parameters and selected safety, efficacy, or PK parameters may be

evaluated and graphically displayed. Further exploratory statistical analyses may be conducted. Biomarker data and analyses may be reported separately.

6.3.2 Pharmacokinetics

Analyses will be performed on the PKS.

The concentration-time courses of rogaratinib in Cycle 1 will be tabulated. The following statistics will be calculated for each of the sampling points: arithmetic mean, standard deviation and coefficient of variation (CV), geometric mean, geometric standard deviation (re-transformed standard deviation of the logarithms) and CV, minimum, median, maximum value and the number of measurements. Means at any time will only be calculated if at least 2/3 of the individual data were measured and were above the lower limit of quantification (LLOQ). For the calculation of the mean value a data point below LLOQ will be substituted by one half of this limit. In tables showing mean values, where values below LLOQ are included in the calculation of mean values, these means will be marked.

Individual and geometric mean concentration vs. time curves of all analytes (using the actual sampling times for individual plots and the planned sampling times for mean plots) will be plotted using both linear and semilogarithmic scale.

PK characteristics (t_{max} , t_{last} , R_{start} , R_{end} , points terminal and %AUC [$t_{last-\infty}$] excluded) will be summarized by the statistics mentioned above. t_{max} and t_{last} will be described utilizing minimum, maximum and median as well as frequency counts.

Concentration data from cycle 2 to 5 of rogaratinib and all concentration data of Atezolizumab will only be listed.

6.4 Safety

Analyses will be performed on the SAF, unless otherwise specified.

Duration of treatment will be summarized using summary statistics. Actual dose, total amount of dose, and percent of planned dose during study period will be also summarized. Dose modification will be summarized.

6.4.1 Determination of MTD

The objective of the dose selection phase is to determine the MTD or confirm that the start dose level of rogaratinib (800 mg b.i.d.) is safe. The MTD is defined as the highest dose that can be given so that toxicity probability is closest to the target toxicity $P_T=30\%$. Estimation of the MTD will be based on the estimation of the observed dose dependent incidence rate of DLT in the first 21 days of dosing.

The modified toxicity probability interval (mTPI) design will be applied to guide the dose selection decisions in the study. The equivalence interval of the toxicity probability for the MTD is set to [25%, 35%], in which any dose with a toxicity probability falling into this interval is considered as an estimate close to the true MTD. The dose selection part will be finished after 20 subjects are evaluable for the MTD assessment. A beta-binomial Bayesian model with Beta(1,1) prior will be used to compute the posterior probabilities that the true rate of DLT is contained in each of the 3 toxicity intervals:

- [0, 25%] under-dosing (below the MTD)
- [25%, 35%] target dosing (close to the MTD)
- [35%, 100%] over-dosing (above the MTD)

Statistical Analysis Plan Supplement

BAY 1163877/19131 Part A

Page: 15 of 18

The mTPI method calculates the unit probability mass (UPM) for above intervals with safety rules to stop due to excessive toxicity. In addition doses that are estimated to have excessive toxicity will be excluded from the trial.

The UPM for a given interval is defined as the probability of the interval divided by the length of the interval. Then an appropriate dose-finding action will be chosen based on the interval with the largest UPM. Specifically, if the UPM for the under-dosing interval is the largest, the dose is considered lower than the MTD and the recommendation is to escalate to the next higher dose (800 mg b.i.d. being the highest possible dose) or to stay on the dose level if current dose is the highest possible dose (letter **E** in [Table 6-1](#)); if the target dosing interval has the largest UPM, the mTPI design will recommend remaining at the current dose (letter **S** in [Table 6-1](#)); if the over-dosing interval has the largest UPM, the design will recommend de-escalating to the previous lower dose (letter **D** in [Table 6-1](#)). If the safety stopping rule is met, the toxicity of the current dose will be considered as unacceptable high and never be used again in the remainder of the trial (letters **DU** in [Table 6-1](#)). The safety rule is triggered if the posterior probability that the current dose is above the MTD is greater than 95%. All of these rules are summarized and precalculated in [Table 6-1](#) below. No decision is made before data of at least 4 subjects are available on the first dose level and are evaluable for DLTs. The sponsor in consultation with the investigators will decide how many additional subjects need to be evaluable for DLTs on the same dose level before the next decision.

The decision on the number of additional subjects and on the next dose level will be based on the recommendations from the mTPI, clinical assessment, all available PK and safety data.

The dose selection part will be finished after 20 subjects are evaluable for DLT assessment and are available for the MTD determination. The RP2D will be defined once sufficient data is available. The final decision about the RP2D will be made by the sponsor in consultation with the investigators.

Statistical Analysis Plan Supplement

BAY 1163877/19131 Part A

Page: 16 of 18

Table 6-1: Possible dose finding actions

Number of subjects with observed DLTs	Number of subjects treated at current dose																
	4	5	6	7	8	9	10	11	12	13	14	15	16	17	18	19	20
0	E	E	E	E	E	E	E	E	E	E	E	E	E	E	E	E	E
1	S	S	E	E	E	E	E	E	E	E	E	E	E	E	E	E	E
2	S	S	S	S	S	S	E	E	E	E	E	E	E	E	E	E	E
3	DU	D	S	S	S	S	S	S	S	S	S	E	E	E	E	E	E
4	DU	DU	DU	D	D	S	S	S	S	S	S	S	S	S	S	S	S
5	DU	DU	DU	DU	DU	D	S	S	S	S	S	S	S	S	S	S	S
6		DU	DU	DU	DU	DU	DU	D	S	S	S	S	S	S	S	S	S
7			DU	D	S	S	S	S	S	S	S						
8				DU	D	S	S	S	S	S							
9					DU	S											
10						DU											
11							DU										
12								DU									
13									DU								
14										DU							
15											DU						
16												DU	DU	DU	DU	DU	DU
17													DU	DU	DU	DU	DU
18														DU	DU	DU	DU
19															DU	DU	
20																DU	

The column represents the number of subjects treated at a given dose level in the trial. Each row represents the number of subjects treated at the dose level and who have experienced dose-limiting toxicity (DLT) events. The letters in each cell provides the dose-assignment decision based on the data readout from the row and column numbers.

E: Escalate to the next higher dose (or stay if current dose is the highest possible dose)

S: Stay at the same dose

D: De-escalate to the previous lower dose (or stop if current dose is lowest possible dose)

DU: De-escalate to the previous lower dose and the current dose will never be used again.

6.4.2 Adverse Events (AEs)

Individual listings of AEs will be provided. AEs will be reported using MedDRA terms (version 20.0 or later) and graded according to NCI CTCAE version 4.03.

AEs will be considered to be treatment-emergent if they have started or worsened after first administration of study drug up to 30 days after the last dose of rogaratinib or 90 days after the last atezolizumab administration, whichever comes later.

The incidence of treatment-emergent adverse events (TEAEs), drug-related adverse events (TEADRs), treatment-emergent and drug-related serious adverse events (SAEs), respectively, will be summarized by MedDRA system organ class and worst NCI-CTCAE grade. TEAEs, SAEs, TEADRs, and drug-related SAEs for events of Grade 3/4/5 will be summarized similarly.

Subject listings of all AEs, SAEs, AESI, TEAEs leading to dose reduction, TEAEs leading to dose interruption, TEAEs leading to discontinuation, AEs leading to DLTs and deaths will be presented. For death, two listings (“during treatment and within 30 days post permanent treatment discontinuation” and “after 30 days post permanent treatment discontinuation”) will be provided.

